3.1.3 Absolute change from baseline

Absolute change from baseline is defined as *(post-baseline value – baseline value)*.

Percent change from baseline is computed as

$100 \times ((\text{post-baseline value} - \text{baseline value}) / \text{baseline value}) \%$.

If either the post-baseline value or the baseline value is missing, then the absolute change from baseline will also be missing. If baseline value is zero, then percent change from baseline will be set to missing.

Unless otherwise specified, “change from baseline” is assumed to be the absolute change from baseline.

3.1.4 Study periods

The following study periods are defined for analysis purposes:

- Screening/run-in period: starting on the date of the first study procedure and ending one day prior to randomisation (for randomised subjects) or on the date of the last study procedure (for screening failures). If any subject is re-screened, the latest available screening will be used for this purpose.
- Planned treatment period (on-treatment and off-treatment): starting on the date of randomisation (efficacy) / date of first dose of IP (safety) and ending on the date of the Week 52 visit or earlier study withdrawal date (for subjects not followed up until Week 52).
- On-treatment period: starting and ending on the start and end dates defined in Section 2.1.5 for efficacy and safety analyses.

- Post-treatment period: starting one day after the end date defined in Section 2.1.5 for efficacy and safety analyses and ending on the study completion or withdrawal date.
- On-study period (planned treatment and follow-up): starting on the date of randomisation (efficacy) / date of first dose of IP (safety) and ending on the study completion or withdrawal date.

3.1.5 Visit windows

All summaries and analyses, both efficacy and safety, which are presented by time point (e.g. “Week 52”) will use a visit window to classify the data record, which is derived from the assessment date relative to the reference start date. This approach allows appropriate classification of visits which may have occurred significantly earlier or later than the protocol assessment schedule, as well as the use of data captured at visits which have no fixed timing (notably the IPD visit), and the handling of data captured at visits for which the database label is incorrect and unresolvable.

Nominal database visit numbers will not be used in any summary or analysis by visit.

For efficacy and safety variables, the reference start date is the date of randomisation, and relative day is therefore defined as $(Date\ of\ assessment - Date\ of\ randomisation) + 1$.

Any data collected at unscheduled or repeat visits will be listed. These data will be included in baseline definitions (see Section 3.1.2) and in any definitions of maximum value, minimum value or last value within the relevant study period.

Data collected at unscheduled or repeat visits will also be included in visit windows, and therefore may be included in summaries or analyses by visit, or used in any sensitivity analyses which involve imputation of data from subjects with non-missing values to subjects with missing values. In the case of a missing value at a scheduled visit, which is then followed by a non-missing value at an unscheduled or repeat assessment within the same visit window, the non-missing value at the unscheduled/repeat assessment will replace the missing value at the scheduled visit.

If a subject has more than one non-missing value within the same visit window, the following rules will apply:

- The non-missing value closest to the target day will be selected for analysis at that visit
- If two non-missing values are the same distance from the target day, the earlier of the two values will be selected for analysis at that visit

- If two non-missing values are recorded on the same day and have a different assessment time associated with both of them, the value with the earliest assessment time will be selected for analysis at that visit
- If two non-missing values are recorded on the same day and have no assessment time associated with at least one of them, or the same assessment time associated with both of them, the average of the two values will be selected for analysis at that visit

If a subject has no value within a particular visit window, then the subject will have a missing value at that visit in summaries and analysis.

The same visit window definitions below will be used regardless of whether the planned treatment period or the on-treatment period is used for analysis (see Section 3.1.4). Each data record in the planned treatment period will be first identified, and then further flagged according to whether it is on-treatment or off-treatment. This flag will be used to select all eligible records for subsequent visit windowing, according to whether the derived visits are to be used in a planned treatment period or an on-treatment period analysis. It should be noted that, if treatment was discontinued within a particular visit window, the rules above for handling multiple values within the same visit window could select a different record according to whether a planned treatment period analysis or an on-treatment period analysis is needed.

In planned treatment period analyses any off-treatment assessments measured at a follow-up visit, which occurred earlier than scheduled follow-up visits Week 58, or Week 64, will be considered in an earlier planned treatment period visit window, where applicable.

Visit windows have been constructed so that every observation collected can be allocated to a particular visit, including unscheduled assessments. No visit windows will be defined for screening visits.

The window for the visits following baseline will be constructed in such a way that the upper limit of the interval falls half way between the two visits (the lower limit of the first post-baseline visit will be Day 2). If an even number of days exists between two consecutive visits, then the upper limit will be taken as the midpoint value minus 1 day. The window for the final scheduled visit collection should extend to the actual assessment date for the visit or to the scheduled study day if the visit is not completed.

For each analysis parameter, the windowing will be based on the protocol-specified schedule of events as defined in Tables 1 and 2 of the protocol.

Table 1 summarises the visits windows corresponding to the full (mostly 4-weekly) protocol scheduling clinic visits.

Table 1 Visit windows

Time point	Target day	Visit Window
Baseline (Week 0)	1	See Section 3.1.2 for baseline definitions
Week 4	29	2-42
Week 8	57	43-70
Week 12	85	71-98
Week 16	113	99-126
Week 20	141	127-154
Week 24	169	155-182
Week 28	197	183-210
Week 32	225	211-238
Week 36	253	239-266
Week 40	281	267-294
Week 44	309	295-322
Week 48	337	323-350
Week 52	365	351-385
Follow-up Week 58	407	386-427
Follow-up Week 64	449	428-469

For the exacerbation-related analyses, no windows will be applied. For endpoints that present visit-based data, the variables will be summarised based on the scheduled days with adjusted analysis-defined visit windows. The adjusted analysis-defined visit windows will be based on the collection schedule listed in the protocol and variables will be windowed to the closest scheduled visit for that variable.

For pre-bronchodilator FEV₁ (L), the non-missing value with acceptable quality (acceptable or borderline quality grade) which is closest to the scheduled visit will be included in the analysis. For post-bronchodilator FEV₁(L), the highest value with acceptable quality from the same date as the pre-bronchodilator FEV₁(L) result will be used. Assessments with missing quality grade will be assumed to have acceptable quality.

For overall analyses not based on any particular study visit (e.g., maximum post-baseline value), all data will be listed and/or analysed, including any repeat or unscheduled visits, unless otherwise specified. For safety endpoints, all post-baseline results will be included in these overall analyses, up to and including the end of treatment Visit 16 (EOT) visit.

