- EXA visit is an optional visit and may be initiated when patient experiences COPD exacerbation. Additional assessments can be performed at the discretion of the PI. If the EXA visit falls within +/- 5 days of the scheduled treatment visit window, the laboratory assessments do not need to be repeated at the next scheduled visit if the same laboratory assessments were already completed at EXA visit, unless at the PI's discretion. Refer to Section 8.1.1.5.
- The sponsor will be blinded to the FeNO values except at screening visit, at any repeat testing that is performed during the screening period and prior to Investigational Product (IP) administration.. The sites will be blinded to FeNO values for the whole study duration.
- d Daily Morning Diary: Nocturnal awakening and items related to: Rescue medication use, major/minor symptoms; Daily Evening Diary: EXACT-PRO/E-RSTM: COPD and items related to: rescue medication and maintenance medication. EXACT-PRO/E-RSTM: COPD is completed daily via e-diary and checked at visits.
- Visit 3 spirometry must be performed on the day of randomization prior to IP administration after appropriate restriction are met as per Section 8.1.2. For every other visit, pre-BD spirometry assessments must be performed only after appropriate restrictions are met as per Section 8.1.2, if not this should be rescheduled to the earliest opportunity within the allowed visit window. Applicable for the COVID-19 pandemic: Spirometry should be performed if allowed and according to local regulations and guidance.
- Pre-BD spirometry (according to separate instruction manual) will be performed at EXA visit as part of induced sputum procedures during treatment phase if subject is participating in the sputum sub study.
- The sponsor and site will be blinded to the immunoglobulin, eosinophil, basophil and monocyte counts from the central laboratory reports except screening visits (Visit 1 and 2), any repeat testing that is performed during the screen visits, and prior to IP administration.
- For WOCBP only, urine HCG test to be done at study site at each treatment visit before the IP administration.

- In case of anaphylaxis additional samples will be taken for serum for immunogenicity.
- The ICF must be signed by the subject prior to the collection of optional pharmacogenetic sample.

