6.5.5 COPD Medication Restrictions on the Days of Scheduled Spirometry and FeNO Visits

Spirometry assessments will be performed at the site at scheduled visits (see Table 1 and Table 2). There are restrictions regarding the subject's COPD medications prior to the spirometry assessments. Please see Section 8.1.2.1.

NOTE: Screening (Visit 1 and Visit 2) and Randomization spirometry and FeNO are not allowed without proper medication wash out.

Screening Visit 1 and Visit 2

Screening lung function assessments can only be done when there are no restrictions to medications (also refer to Section 8.1.3) and Visit 1 SARS-CoV-2 naso/oropharyngeal swab test (or rapid test) result is negative. If the SARS-CoV-2 naso/oropharyngeal swab test (or rapid test) result will not be available on the day of Visit 1, the screening lung function

assessments must be postponed until next visit, the postponed Visit 1, after the SARS-CoV-2 naso/oropharyngeal) swab test (or rapid test) result is confirmed negative.

At the postponed Visit 1, the spirometry equipment will allow pre-BD, post-BD spirometry, FeNO and ECG (combined Visit 1 and Visit 2) to be performed. Visit 2 should be scheduled, if the Visit 2 post-BD spirometry and FeNO were not done at the postponed Visit 1. Preferably, Visit 2 should be scheduled no later than 1 week after Visit 1 but the enrolment can be extended to accommodate additional waiting time required to obtain Visit 1 SARS-CoV-2 naso/oropharyngeal swab test result. The subject must meet the COPD medications restrictions in order to perform the lung assessments.

Subjects will be asked to withhold their triple inhaled (ICS/LABA/LAMA) medications on the morning of the screening pre-BD and post-BD spirometry and FeNO (should be at least 12 hours prior to the assessment for twice daily medication and for 24 hours prior to the assessment for once daily medications) for the eligibility assessment (see Section 5.1, inclusion criterion 7). In addition, SABA and SAMA should not be used within 6 hours of this spirometry and FeNO assessment. The subject's usual COPD medications may be administered following completion of the screening lung function procedures.

Treatment Visits 3-15

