Subjects will be asked to withhold their usual triple inhaled (ICS/LABA/LAMA) medications on the mornings of the scheduled spirometry and FeNO visits and preferably for at least 12 hours prior to the spirometry and FeNO assessment (for medications that are administered twice daily)/24 hours prior to the assessment (for once daily medications). This is especially important prior to scheduled spirometry and FeNO assessments (see Table 1 and Table 2) in order to maintain the integrity of planned efficacy analyses around lung function improvement. In addition, SABA and SAMA should not be used within 6 hours prior to the spirometry assessments. The subject's usual COPD medications may be administered following completion of the post-BD spirograms or sputum post-BD spirograms (for patients participating in sputum sub-study). The IP will be administered at a scheduled visit after the pulmonary lung function assessments.

If the subject has taken their usual triple inhaled (ICS/LABA/LAMA) medications on the morning of the scheduled spirometry and FeNO visit, the Investigator/authorized delegate should remind the subject of the importance of withholding their usual morning maintenance therapy, and reschedule the visit for another day, within the allowed window. If rescheduling is absolutely not feasible for the subject, spirometry and FeNO may be performed with a notation indicating that spirometry and FeNO was performed without proper washout of the usual triple inhaled (ICS/LABA/LAMA) medications. Exception is randomization visit, which must be performed when medications restrictions are met.

If the subject has taken the rescue SABA and/or SAMA within 6 hours of the planned site visit spirometry they should ideally remain at the site until such time that the 6 hours withholding time has been reached if it does not exceed the 1.5-hour spirometry window or return on another day, within the visit window. If neither of options is feasible for the subject, spirometry may be performed with a notation indicating that spirometry was conducted within 6 hours of SABA and/or SAMA use.

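### The SAP picks pre-bronchodilator FEV1 without using the recorded washout status, so a reading flagged as not washed out can be analysed as pre-bronchodilator (minor)

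*SAP*

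**What the plan says.** SAP section 3.1.5 states that for pre-bronchodilator FEV1 "the non-missing value with acceptable quality (acceptable or borderline quality grade) which is closest to the scheduled visit will be included in the analysis". A missing quality grade counts as acceptable. The same section puts unscheduled and repeat readings into the windows, sets nominal visit numbers aside, and settles multiple values by distance from the target day, then by the earlier value.

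The protocol restricts bronchodilators before spirometry, and section 6.5.5 gives protection of the lung function analyses as the reason. Under the sub-heading "Treatment Visits 3-15" it nevertheless allows two departures. If maintenance therapy was taken and rescheduling is not feasible, "spirometry and FeNO may be performed with a notation indicating that spirometry and FeNO was performed without proper washout". If rescue medication was used and neither waiting nor returning is feasible, "spirometry may be performed with a notation indicating that spirometry was conducted within 6 hours of SABA and/or SAMA use". Baseline is treated differently: "Exception is randomization visit, which must be performed when medications restrictions are met".

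At unscheduled and exacerbation visits the restrictions are discretionary, and medication timing is to be recorded (section 6.5.6). Exacerbation-visit spirometry without withholding is to carry a notation (section 8.1.1.5).

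Footnote e of the protocol's Table 2 is stricter for visits after randomisation: "pre-BD spirometry assessments must be performed only after appropriate restrictions are met as per Section 8.1.2, if not this should be rescheduled".

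**The concern.** The protocol has sites record which readings were not washed out, and the analysis rule makes no use of that record. A reading taken after a bronchodilator does not measure pre-bronchodilator FEV1. Subtracting a washed-out baseline from it adds a drug effect unrelated to the investigational product. If such readings are more frequent in one arm, for instance because rescue use follows symptoms, the treatment difference at that visit shifts. If they are equally frequent, they add noise. At stake are the by-visit differences and p-values that SAP section 4.2.5.5 reports for a secondary endpoint.

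**Working it through.** **1. Is washout used anywhere in the analysis?** I looked at each place where it could enter.

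- Selection (SAP 3.1.5): non-missing, graded acceptable or borderline (or ungraded), closest, then earliest. No washout term.
- Derivation (SAP 3.2.2.5): change from baseline only.
- Model (SAP 4.2.5.5): MMRM on post-baseline values, with no washout term or exclusion.
- Missing-data sensitivity analyses (SAP Appendix 8.2): driven by the reason for dropout.
- Deviations (SAP 2.2): important deviations remove no data.

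So a flagged reading that is the only one in its window is analysed. Protocol Table 2 schedules post-baseline pre-bronchodilator spirometry at Visits 4, 6, 9, 13 and 16 (Weeks 4, 12, 24, 40 and 52). The section 6.5.5 allowance sits under Visits 3 to 15, and randomisation is excepted. The direct exposure is therefore Weeks 4, 12, 24 and 40.

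**2. Windows.** Target day = 7 × week + 1; upper limit = midpoint to the next target day, minus 1. This reproduces all 14 limits in SAP Table 1 from Week 4 to Week 58. For example, Week 52 starts after (337 + 365)/2 − 1 = 350 and ends at (365 + 407)/2 − 1 = 385. The SAP windows each variable to its own schedule, so for FEV1:

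| Visit | Target day | Window |
|---|---|---|
| Week 4 | 29 | 2–56 |
| Week 12 | 85 | 57–126 |
| Week 24 | 169 | 127–224 |
| Week 40 | 281 | 225–322 |
| Week 52 | 365 | 323–385 |

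The Week 52 upper limit may instead be the actual or scheduled visit day, because that is the last FEV1 collection. Either way the windows are wide enough to hold a second reading.

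**3. Can a flagged reading displace a washed-out one?** Take a discretionary unscheduled reading on Day 364, not washed out, and a washed-out Visit 16 reading on Day 369 (within the ±5-day visit window). Distances from Day 365 are 1 and 4 days, so the rule takes Day 364. If washout were considered first, it would take Day 369.

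**4. Size.** The documents give no flagged share and no carry-over, so every input here is an assumption.

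At one visit, shift in the treatment difference = carry-over × difference between arms in flagged share:

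| Carry-over | 0 points | 5 points | 10 points |
|---|---|---|---|
| 50 mL | 0 mL | 2.5 mL | 5 mL |
| 100 mL | 0 mL | 5 mL | 10 mL |
| 200 mL | 0 mL | 10 mL | 20 mL |

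The sign depends on which arm has more flagged readings.

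Flagged readings at Weeks 4 to 40 reach the Week 52 estimate only through subjects with no Week 52 value. Shift = carry-over × fraction missing Week 52 × W × d. Here W is the sum of the regression weights of Week 52 on the earlier visits. The term d is the excess flagged share in subjects who miss Week 52 over those who do not, present in one arm only.

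- AR(1), correlation 0.6 to 0.8: W = 0.60 to 0.80.
- Compound symmetry, four earlier visits: W = 4ρ/(1 + 3ρ) = 2.4/2.8 = 0.86 to 3.2/3.4 = 0.94.
- With 10% missing and d = 10 points: 50 mL × 0.10 × 0.60 × 0.10 = 0.3 mL, up to 200 mL × 0.10 × 0.94 × 0.10 = 1.9 mL. With d = 0 the shift is 0.

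**The case against.** The strongest reply is that this will seldom happen and matters little. Section 6.5.5 allows an unwashed scheduled test only when the alternatives are not feasible, so such a reading normally has no washed-out partner in its window. Table 2 schedules no spirometry at unscheduled visits. The exacerbation visit is optional, and its pre-bronchodilator test "will be performed at EXA visit as part of induced sputum procedures during treatment phase if subject is participating in the sputum sub study". The phrase in SAP 4.2.5.5 limiting the model to visits specified in the protocol could be read as keeping unscheduled readings out. The endpoint is secondary, is read at Week 52, and has nominal p-values. The quality grade is defined in a spirometry manual (protocol 8.1.2.1) that may already deal with washout. A flagged test may also be counted as a procedural deviation, since SAP 2.2 and 4.2.1 tabulate important deviations by arm.

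Most of this stands, and it sets the severity. Displacement is a possibility under the written rules, not an expected event. The reply about visits specified in the protocol is weaker, because SAP 3.1.5 expressly admits unscheduled readings and discards nominal visit labels. The replies on the quality grade and the deviation table cannot be settled here: neither document says that the grade covers washout or that such tests count as important deviations, and an ungraded reading passes anyway. None of these replies touches the lone flagged reading at a scheduled visit.

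**Conclusion.** The gap is real and minor. SAP 3.1.5 ignores information that the protocol collects to protect this endpoint. The clear consequence is that lone flagged readings at Weeks 4, 12, 24 and 40 can be analysed as pre-bronchodilator FEV1. The size is unknown: no bias in the treatment difference if flagged shares are equal, and 0 to 20 mL at a visit over the assumed ranges. Carry-over to Week 52 is about 0 to 2 mL on the assumptions shown. The primary endpoint is unaffected.

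A reader might infer more, in four ways that the documents do not support:

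- **Two readings on one day.** One might think that section 6.5.5 produces an early unwashed test and a later washed-out one, with the SAP taking the earlier. The text says of subjects who used rescue medication that "they should ideally remain at the site until such time that the 6 hours withholding time has been reached", and only within the 1.5-hour spirometry window. That is waiting before a test; no test before the wait is prescribed.
- **A known bias at Week 52 from exacerbation visits.** A bronchodilator would raise FEV1 while the acute worsening could lower it, so neither the direction nor an upper bound is established.
- **An effect on clinically important deterioration.** That endpoint is exploratory, SAP 3.2.3.2 does not say that it uses windowed values, and no between-arm effect follows.
- **That flagged readings would go uncounted.** A deviation table might show them. The documents simply do not say.

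**What to change.** 1. In SAP 3.1.5, when a window holds more than one acceptable pre-bronchodilator FEV1 value, select a reading with washout met over one flagged as not met, before applying closeness or earliest time.
2. Keep a lone flagged reading in the main MMRM, in line with the SAP's use of all available data (2.1.5) and its rule against excluding data for deviations (2.2). Pre-specify one sensitivity MMRM for pre-bronchodilator FEV1 with flagged readings set to missing.
3. Tabulate flagged readings by arm and visit.
4. Before database lock, confirm that the notation is in the analysis database and whether the quality grade already covers washout.

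Protocol Table 2 footnote e and section 6.5.5 must also be reconciled, including for Visit 16: the footnote requires the restrictions to be met or the test rescheduled, while section 6.5.5 lets the test proceed with a notation, under a sub-heading that stops at Visit 15.

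The cost is a few lines of SAP text, one count table and one extra model run. If the notation exists only in source notes, it would have to be retrieved before lock. The downside is a few more missing values, possibly informative and handled under missing at random, in the sensitivity analysis only.
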